4.4 Sample size calculation

The primary objective of this study is to demonstrate that treatment with MagnetOsTM Granules is non-inferior to autograft to obtain bony fusion in the spine. The primary outcome is the rate of successful posterolateral bony fusion after one year, assessed at CT-scans. Fusion will be scored binomially and non-inferiority of fusion in the MagnetOs condition will be assessed using a McNemar's test.

Based on literature^{6,28-30,34} and the preliminary results of the AxA study, we estimate a fusion percentage of 50% for unilateral grafting after one year, and a 70% concordance between the left and right side of the fusion trajectory (i.e. both sides fused or non-fused). The non-

inferiority margin is set at an absolute 15% less effectiveness in the MagnetOs condition after one year, which corresponds with 15% less posterolateral sides that are judged as fused. In other words, the rate of fused posterolateral sides in the MagnetOs condition should be more than 35% if the autograft condition shows 50% fusion. We argued that the percentage of the iliac crest graft related complications, ranging from 5% major complications to 40% minor complications, may justify 15% less fusion in a condition that eliminates these complications.

Based on a 1:1 paired assignment of MagnetOsTM Granules to the control condition with autograft, a power of 80%, a one-sided alpha of 0.05 and the non-inferiority margin of 15%, the required sample size for the primary outcome is 84 patients (see Appendix A). We assume that approximately 15% of the included patients will not be evaluable after one year. The intra-patient analyses are not possible when the fusion area has to be revised or when a deep wound infection has occurred and considerable amounts of graft material have to be removed (expected percentage 2-5%). Other failures are lost to follow-up or bad scan quality. Therefore, the total number of patients to be enrolled will be 100.

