9.1 Primary efficacy analysis

For the primary efficacy analysis, a comparison will be made between the fusion performance of the MagnetOsTM condition and the autograft condition, scored from the one-year (12-15 months) CT-scans according to the method described in Appendix C. Patients that required revision surgery influencing the fusion will be excluded from this analysis. In addition, if one side of a fusion-level is considered not evaluable, this level will be excluded. All evaluable scores will be dichotomized into fusion and no fusion. To allow inclusion of patients with fusion of multiple segments, without increasing the influence of these patients on the outcome, each side in these patients will be statistically considered as one condition. This means that the possible outcomes in these patients are: no fusion (if none of the levels is fused), equal fusion (if an equal number of segments is fused per side) or fusion at one side vs. no-fusion at the other side in case one side contains more fused segments than the other side.

The basis for the primary efficacy analysis will be the test of non-inferiority by performing a McNemar's test. The null hypothesis is that inferiority in fusion rate of the MagnetOsTM Granules compared to the autograft condition is greater than 15% (PAG-PMAG \geq 15%); the alternative hypothesis is that the MagnetOsTM Granules fusion rate will not be lower than the autograft success rate by more than 15% (PAG-PMAG< 15%).

In addition to the McNemar's test, a generalized estimating equations (GEE) model will be used to examine fusion on each side of a vertebra, while accounting for clustering of vertebrae within patients. The outcome will be fusion (yes/no) and the explanatory variable will be treatment. Analysis will result in an odds ratio for MagnetOsTM Granules vs. autograft and a 95% confidence interval.

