The CT score will be dichotomized into fused and not fused. To allow the inclusion of patients with intended fusion of multiple segments, the sum of fusions on each side of the spine of these patients will be compared. If one side of a fusion-level is considered not evaluable, this will be excluded as well as the contralateral level. In multilevel patients, superiority (in number of fused levels) of one side, will be considered fusion and the other side non-fusion to prevent an unequal influence of patients with multi-level fusions. Although fusion assessment by this method gives more a "relative performance score" than a "fusion rate," analyzing the fusion rate of individual levels will not be adequate. There is strong reason to believe that the fusion rate will vary from patient to patient, so the fusion of individual vertebrae from one patient will not be independent. Since the study is randomized, this dependence should have no effect on a point estimate for the difference in fusion rates for MagnetOsTM Granules vs. autograft, but will certainly affect the standard error of the difference, thereby making standard statistical inference unreliable.

Although we know of no way of generating correct p-values or confidence intervals for differences in fusion rates using clustered data, it is possible to use a multi-level model (in which the clustering of vertebrae within patients is taken into account) to examine the effect of MagnetOsTM Granules and autograft on fusion, and using the vertebrae as the primary level of analysis. Such a model will produce an odds ratio instead of a difference in fusion rates. Since a sample size calculation based on a multi-level analysis requires a number of assumptions that cannot be supported by current data, we decided to perform sample size calculation based on the McNemar's test, and to use the multi-level model as a secondary analysis since it will make better use of the complete data while correctly taking the clustering into account.

Secondary Analysis

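### The secondary level-by-level GEE reports only an odds ratio, so no level-based fusion-rate difference is set beside the 15-point margin, and the reason Appendix A gives is mistaken

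*Combined protocol and SAP*

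**What the plan says.** Section 4.4 puts the margin on the absolute scale: the non-"inferiority margin is set at an absolute 15% less effectiveness in the MagnetOs condition after one year". It sizes the trial for "a power of 80%, a one-sided alpha of 0.05 and the non-inferiority margin of 15"%. Section 9.1 states the alternative hypothesis on the same scale, that the MagnetOs "fusion rate will not be lower than the autograft success rate by more than 15"%, and makes a McNemar-type test the basis of the primary efficacy analysis.

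Section 9.1 then adds a GEE on fusion at each side of each vertebra, with treatment as the explanatory variable. Its output is fixed: "Analysis will result in an odds ratio for" MagnetOs against autograft, with a 95% interval. Appendix A repeats this under its secondary analysis and gives the reasoning under its primary analysis. Dependence between levels should not disturb the point estimate of the difference but does disturb its standard error; "we know of no way of generating correct p-values or confidence intervals for differences in fusion rates using clustered data"; a multi-level model is therefore used, and "Such a model will produce an odds ratio instead of a difference in fusion rates".

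Appendix A also says that this model uses the full data better than the patient-level score does. It concedes that the patient-level score measures how one side does relative to the other more than it measures a rate of fusion.

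**The concern.** The hypothesis and its supporting model are on different scales. No odds-ratio margin, conversion to a difference, or rule for reading the GEE against the hypothesis is given, and the 95% interval does not match a one-sided 5% test.

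This matters because of what the primary score measures. In a multilevel patient, the side with more fused levels counts as fused and the other as not fused. A patient with 3 of 4 levels fused on one side and 2 of 4 on the other is scored as fusion against non-fusion. The level-based model is the planned analysis that could show the actual difference in fusion rates, with its uncertainty, next to 15 points. As written it does not. The reason given for leaving the difference out is a supposed lack of method, which can be checked.

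**Working it through.** **1. The plan's own figure.** Inputs from section 4.4 and Appendix A: margin 0.15, both rates 0.50, discordance 0.30 (1 - 0.70 concordance), one-sided alpha 0.05, power 80%. Exact enumeration of the paired-proportion score test with restricted-likelihood variance gives power 0.80098 at N = 84, as in the Appendix A table. The simple Wald formula gives (1.645 + 0.842)² × 0.30 / 0.15² = 82.4. Allowing for 15% not evaluable, 84 / 0.85 = 98.8, consistent with 100 enrolled. The sample size stands.

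**2. The margin as an odds ratio.** For autograft rate p, a 15-point deficit corresponds to OR = [(p - 0.15)/(1.15 - p)] / [p/(1 - p)].

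| Autograft rate | OR equal to -15 points |
|---|---|
| 30% | 0.41 |
| 40% | 0.50 |
| 50% | 0.54 |
| 60% | 0.55 |
| 70% | 0.52 |
| 80% | 0.46 |
| 90% | 0.33 |

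Conversely, an OR of 0.538 (35% against 50%) is a difference of -11.3 points at 30%, -15.0 at 50%, -15.3 at 60% and -11.7 at 80%. The 50% rate is a planning estimate ("we estimate a fusion percentage of 50% for unilateral grafting after one year").

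**3. A conservative bound.** Over all autograft rates, the largest deficit compatible with a given OR is (1 - √OR)/(1 + √OR). Setting this to 0.15 gives √OR = 0.85/1.15 = 0.739, so OR = 0.546. A lower limit above about 0.55 excludes a 15-point deficit at any rate. Below that, the answer depends on the autograft rate.

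**4. A difference with a clustered interval.** For patient i, let K_i be the evaluable levels and S_i the fused MagnetOs levels minus the fused autograft levels. The level-based difference is e = ΣS_i / ΣK_i. Leaving out one patient at a time gives e_(i) = (ΣS - S_i)/(ΣK - K_i), and SE = √[((n - 1)/n) Σ(e_(i) - e)²], with a t reference on n - 1 degrees of freedom. Equivalently, with treatment as the only covariate, the planned logit GEE already estimates both marginal rates and their covariance. The delta method then gives the difference and its interval. If the odds-ratio interval handles the clustering properly, so does this one.

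**5. Performance at this trial's size.** The documents do not give the spread of levels per patient or the correlation structure. Assumed: 85 patients, 1 to 6 levels, 35% to 50% of patients with one level, patient variance share 0.2 to 0.5, level share 0.2 to 0.4 (simulated level-wise concordance about 65% to 82%).

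- Patient-clustered robust 95% intervals covered 94.0% to 94.9%. Across the simulations run, the one-sided size at a true -15 points was about 5.4% to 6.1%.
- Jackknife-t 95% intervals covered 94.7% to 95.3%, with one-sided size 4.9% to 5.6%.
- In 400 simulated trials with no true difference, the identity-link GEE and the logit GEE with delta method agreed: mean SE 0.0391 for both, empirical SD 0.0399, coverage 93.75%.
- Intervals that treat all observations as independent covered 98% to 99.9% instead of 95%. The plan is right that ordinary inference is unreliable here.

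These GEE fits used one exchangeable correlation within patient, not the three-level structure of Appendix A.

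**6. What the gap looks like.** Take an observed 8-point level-based deficit (42% against 50%) with SE 0.0391. The 95% interval is -0.08 ± 1.96 × 0.0391, or -15.7 to -0.3 points. The 90% lower limit is -0.08 - 1.645 × 0.0391, or -14.4 points. The OR is 0.42/0.58 = 0.724. Its log-scale SE is roughly 0.0391/0.247 = 0.158 (0.247 being the mean of p(1 - p)), so its 95% lower limit is about exp(-0.323 - 0.310) = 0.53. The planned output would show MagnetOs significantly worse, with a lower limit just under 0.546. At the trial's own one-sided 5% level, the difference would clear the margin.

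**The case against.** The best defence is that the GEE is not the non-inferiority test. Section 9.1 adds it to the McNemar-type test, Appendix A calls it secondary, and a supportive model needs no margin. This stands, and it limits the point to reporting. The odds ratio also has other planned uses in section 9.3, which is a reason to keep it.

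Several stronger readings are tempting and are not supported:

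- A reader might infer that an odds ratio can neither support nor contradict the claim. Step 3 shows otherwise: a high enough lower limit excludes the deficit at every rate.
- A reader might infer that the GEE is the only analysis using all levels. The primary score also uses every evaluable level, through the sum on each side. It collapses them within patient.
- A reader might infer that the plan asserts that no valid interval exists. It says only that the authors know of none, and it bases the sample size on McNemar for a separate reason: the assumptions that a multi-level calculation would need.
- A reader might fear that an interval including 1 will be declared non-inferiority. Nothing in the documents says so.

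Two further objections shape the remedy. A level-based difference gives multilevel patients more weight, which the primary analysis deliberately avoids, so judging it formally against -15 points would create a second verdict on another estimand. Uncorrected robust intervals are also slightly liberal. Both objections stand.

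**Conclusion.** The point holds as a gap in a secondary analysis and a mistaken methodological premise. The non-inferiority decision, its alpha and N = 84 are untouched, and a reader who inferred that the primary conclusion is unsafe for this reason would go beyond the documents. What is lost is a level-based difference in fusion rates, with an interval, next to the margin. The odds ratio replaces it imperfectly, since the value equal to -15 points runs from 0.33 to 0.55 over autograft rates of 30% to 90%. The odds-ratio figures and the bound of 0.546 are plain arithmetic. The near-nominal performance of the clustered interval rests on the assumed level mixes and variance shares, and was not checked under the exact three-level working correlation.

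**What to change.** In section 9.1 and Appendix A:

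- Add the level-based MagnetOs minus autograft risk difference, from an identity-link GEE or as the marginal difference from the planned logit GEE.
- Use errors clustered on patient, a small-sample correction (for example the jackknife with a t reference) and a two-sided 90% interval, which matches the one-sided 5% test.
- Show it beside -15 points as a supportive analysis. State that the primary test alone decides non-inferiority and that the level-based estimate gives multilevel patients more weight.
- Keep the odds ratio and its 95% interval as descriptive.
- Replace the Appendix A sentence that no method is known with a reference to the method chosen.

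The cost is wording and a little extra analysis, with no new data and no change in sample size. The downside is that the supportive result may differ from the primary one, so its role should be fixed before the one-year data are analysed.

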APPENDIX B. SUGGESTED SURGICAL TECHNIQUE

Step 1: Patient positioning

The patient is placed in the prone position. To avoid abdominal compression, separate rolls or specific frames can be used. Preferably a foil skin drape is used.

Step 2: Exposure

After sterile draping, a single midline incision centered on the intended fusion area is made in both the skin and the fascia. The paraspinal muscles are subperiosteally stripped from the spinous processes and retracted laterally. The facet joints and transverse processes are exposed.

Step 3: Instrumentation

After partial removal of the involved facet joints, the surgeon determines the exact surgical procedure concerning the insertion of the instrumentation. Depending on the surgeon's preference, pedicle screws can be inserted now or after decompression. The rod fixation can be inserted at this time or after placement of the graft.

Step 4: Decompression

If necessary, a decompression of the posterior spine is performed according the surgeon's preference. The decompression may involve a whole or partial laminectomy and may include one or more levels.

Step 5: Decortication

The next step is meticulous and thorough decortication of all of the available cortical surfaces, including the dorsal, superior and inferior surfaces of the transverse processes. It may be necessary to extend the longitudinal incision to get good exposure! In addition, the dorsal and lateral aspects of the lamina and pars interarticularis, from the most proximal vertebra to the most distal vertebra to be included in the fusion should be denuded. If the facet joints remain, these should be prepared for fusion by removing the exposed articular surfaces.

Step 6: Graft preparation and volume measurement

All bone obtained from decompression and decortication is stripped from soft tissue and morcellized to 2-4mm pieces. The volume is assessed by slight compression in a 20mL syringe.

Step X: Additional interbody fusion procedure

According to the surgeon's preference, an interbody cage can be used (PLIF or TLIF). This cage is preferably filled with local autograft bone and positioned before disclosure of the randomized allocation. If the surgeon prefers iliac graft bone, both sides of the spine have to be prepared for posterolateral bone grafting before the allocated side of the autograft (and bone graft harvesting) is disclosed.

Step 7: Disclosure of the random allocation

After instrumentation and preparation of the fusion trajectory the envelope containing the allocation side of the autograft and MagnetOs condition and thereby the allocation of the iliac harvesting side, is opened.

Step 8: Harvesting of iliac crest autograft

Only one side of the pelvis can be used for iliac crest bone harvesting. This must be the same side as allocated to the autograft posterolateral spine fusion condition. The surgeon can use any technique that exposes the iliac crest to obtain corticocancellous bone, but preferably no additional skin incision is made and harvesting through a posterior cortical window is advised. A total autograft volume of 8-10cc per side and fusion level is intended. The contribution of iliac bone graft to this volume has to be at least 50%. For example in a L3-S1 three-level fusion with 10cc of local bone, another 20cc of bone from the iliac crest is required to reach 3x10cc. If local bone is 20cc, 5cc of this will not be used as local bone can only be 15cc (= 50% of 30cc). If the 10cc per level and side cannot be reached because of limited iliac bone graft, the autograft volume has to be extended with local bone. In case the volume remains below 8cc per side, this is accepted as a consequence of autologous bone grafting. The MagnetOs condition will always be 8-10cc and not combined with local bone.

Step 9: Placement of the graft

Both grafts, the autograft and MagnetOsTM granules, are placed on the allocated side around the instrumentation and in the decorticated lateral gutters, bridging the dorsal surfaces of the transverse processes, facets and laminae. No graft is placed on the dura. No additional substances like blood or bone marrow are added. If not yet done at step 3, the rod fixation is inserted at this time.

Step 10: Patient closing

The patient is closed using the technique preferred by the surgeon. If vancomycin or another antiseptic procedure is used, this should be recorded on the surgical form of the CRF.

APPENDIX C. CT ASSESSMENT

Aim

To compare the fusion rate of the MagnetOsTM granules side to the autograft side after 1 and 2 years, by using CT-scans.

Method primary analysis

For the primary analysis, all included patients will be CT-scanned at the treating center. The CT-scan will be scheduled at 12-15 months after surgery. The standard local protocol for the spine will be used when this provides a slice thickness of ≤ 1 mm. Otherwise, the slice thickness will be adapted. To allow all desired planar reconstructions, the data will be captured and stored as volume scans. The raw volume dataset (DICOM scans), and preferably reconstructions in the coronal, sagittal and axial, will be de-identified and stored on a CD-ROM and send to the principal investigator for assessment by a panel consisting of at least one spine surgeon and an uninvolved specialist. Based on literature review and experience with the AxA trial we developed the following protocol.

Stepwise protocol

- All patients will be scanned with a volume scan with ≤ 1 mm slice thickness;
- Data will be captured and stored as volume scans;
- All scans will be assessed independently by at least two observers, blinded to the treatment allocation;
- First, the fusion level and side will be identified and assessed in three planes: coronal, sagittal and axial;
- Osteotomized segments will be excluded from the analyses. If one side of a fusion-level is considered not evaluable, this level will be excluded as well;
- If obvious indications of mobility like material failure or apparent pseudoarthrosis exist, the level will be considered a non-union;
- If not, the presence of an obvious bone bridge/fusion between the posterolateral vertebra will be determined;
- Fusion is scored based on assessment in three planes and at two locations, to indicate the probability that the bony bridge is graft related:
 - Likely graft related is a bony bridge between the transverse process and >1 mm lateral or above the rod;
 - Probably not graft related is a bone bridge directly around the rod, between the lamina or fusion of the facet joints;

- An obvious fusion at any of these locations in each plane is scored 2 points, doubtful fusion is 1 point and non-union is 0 points;
- If the segment is fused in at least one plane (2 points) and does not show obvious absence of fusion in both the other planes (scores at least 1 in at least one of the other planes) it is regarded as fused;
- The points of the graft related and non-graft related locations cannot be accumulated;
- Finally, the presence of an interbody fusion as a result of an interbody fusion device will be determined in two planes and scored similarly (fusion is at least 3 points).

In case of disagreement on overall fusion between the observers, a third investigator will be counseled to get consensus. If disagreement persists, the fusion will be scored as doubtful.

Method secondary analysis

For the other secondary analyses, the 2 year CT-scans will be assessed similarly.
